## 2.2 Secondary Objectives/Endpoints

### Feasibility:

- Technical success of the cTACE procedure (technical failure is defined as the inability to administer the cTACE material, in which case the patient would be excluded from the study)
- Dose of doxorubicin delivered

### Safety:

- All toxicities assessed as being at least possibly related, up to the 3-4 week follow-up visit (post cTACE) will be collected. Toxicities will be analyzed by descriptive statistics to show type, grade (NCI Common Toxicity Criteria v4.0), frequency and time from cTACE.

## 3. Subject Selection

### 3.1 Subject Selection

Patients must have histologically, cytologically, or radiologically confirmed liver dominant or liver only malignancy. Patients must have an ECOG performance status of 0-1 at study entry and maintain a Child-Pugh class of A-B without significant liver decompensation (see Tables below). There must be measurable or evaluable disease that will be directly treated with intrahepatic therapy (as defined by Response Evaluation Criteria in Solid Tumors [RECIST] 1.1).

GRADE	ECOG PERFORMANCE STATUS
0	Fully active, able to carry on all pre-disease performance without restriction
1	Restricted in physically strenuous activity but ambulatory and able to carry out work of a light or sedentary nature, e.g., light house work, office work
2	Ambulatory and capable of all self-care but unable to carry out any work activities; up and about more than 50% of waking hours
3	Capable of only limited self-care; confined to bed or chair more than 50% of waking hours
4	Completely disabled; cannot carry on any self-care; totally confined to bed or chair
5	Death

**ECOG Performance Status:** describes a patient's functional level in terms of self-care and physical activity.

Parameter	Points Assigned		
	1	2	3
Ascites	Absent	Slight	Moderate
Bilirubin, mg/dL	≤ 2	2-3	> 3
Albumin, G/dL	> 3.5	2.8-3.5	< 2.8
Prothrombin Time			
Seconds over control	1-3	4-6	> 6
INR	< 1.7	1.8-2.3	> 2.3
Encephalopathy	None	Grade 1-2	Grade 3-4

**Child-Pugh Classification of Liver Disease Severity:** Modified Child-Pugh classification of liver disease severity according to the degree of ascites, the plasma concentrations of bilirubin and albumin, the prothrombin time, and the degree of encephalopathy. A total score of 5-6 is considered grade A (well-compensated disease); 7-9 is grade B (significant functional compromise); and 10-15 is grade C (decompensated disease). These grades correlate with one-year and two-year percent survival; grade A – 100 and 85 percent; grade B – 80 and 60 percent; and grade C – 45 and 35 percent, respectively.

### 3.2 Inclusion Criteria

Inclusion criteria as follows:

1. Patient's age is ≥ 18 years.
2. Histologically, cytologically, or radiologically confirmed liver dominant or liver only malignancy.
3. Preserved liver function (Child-Pugh A-B class) without significant liver decompensation.
4. Eastern Cooperative Oncology Group (ECOG) performance status of 0-1 at study entry.
5. Measurable or evaluable disease that will be directly treated with intrahepatic therapy (as defined by Response Evaluation Criteria in Solid Tumors [RECIST] 1.1).

6. Suitable for TACE, based on blood parameters such as platelet count, bilirubin, and international normalized ratio.
7. May be enrolled with a history of prior liver directed chemoembolization if chemoembolization to the target lesion occurred > 1 year prior to enrollment date. TACE to different targets within 1 year prior to enrollment date, radioembolization to target location, or other form of intra-arterial therapy will not exclude subjects.

### 3.3 Exclusion Criteria

Exclusion criteria as follows:

1. Serum total bilirubin > 3.0 mg/dL.
2. Creatinine > 2.0 mg/dL
3. Platelets < 50000/ $\mu$ L
4. Complete portal vein thrombosis with reversal of flow.
5. Ascites (trace ascites on imaging is acceptable).

### 3.4 Inclusion of Women and Minorities

All patients, regardless of sex or ethnicity, presenting for cTACE for primary or secondary liver cancer will be reviewed for study eligibility. For participants who are not fluent in spoken or written English, interpreter services will be available both during the informed consent process and during the subject's participation as needed. A translated short form consent will be provided.

## 4. Subject Registration Procedures

### 4.1 General Guidelines

All patients would be seen for an initial visit at the Interventional Radiology clinics, where a clinician would present all treatment options. If the patient expresses an interest in the study, a member of the study team designated to consent patients would discuss the protocol in greater detail explaining the risks and benefits of the study, and obtain informed consent from the patient or a legally acceptable representative. Imaging, laboratory results, and medical history will be used as part of the screening process to determine the patient's eligibility for the study.

### 4.2 Registration Process

Patients consented for the study will be registered with OnCore, Yale's Clinical Trials Management System, and be assigned a study identifier and counted for the final data analysis. Patients' progress while on the study will be managed via OnCore.

### 4.3 Screening Assessments

Assessment completed in the initial clinic visits (pre-consent), as part of standard of care assessments, may be used as part of the study screening assessment.

- Detailed medical history including previous cancer history and cancer treatment. Any additional relevant medication taken one year prior to study start will also be recorded.
- History and physical exam (including vital signs, ECOG-PS assessment, height, weight) within 30 days of cTACE.
- Chemistry panel: Aspartate aminotransferase (AST), alanine aminotransferase (ALT), bilirubin (total and direct), alkaline phosphatase (AP), total protein, albumin, calcium, phosphate, glucose, creatinine, blood urea nitrogen (BUN).
- Electrolyte panel: sodium, potassium, chloride.
- Complete blood count: hemoglobin, hematocrit, platelet count, white blood cell count (WBC). WBC should include differential neutrophil, lymphocyte, monocyte, basophil, and eosinophil counts.
- Prothrombin time and INR.
- Appropriate tumor marker: alpha feto-protein (AFP), carcinoembryonic antigen (CEA), CA 19-9, etc.
- Serum or urine pregnancy test for women of childbearing potential (must be negative)
- Contrast enhanced MRI of the liver within 30 days of treatment. A CT may be used if a MRI would be improbable to obtain.

## 5. Study Design/Investigational Plan

### 5.1 Overall Design

The study is a single site, prospective study, designed to measure the PK of doxorubicin and its metabolite doxorubicinol at various timed intervals after cTACE in patients with primary or metastatic liver cancer.

Up to 30 patients will be enrolled that meet study entry criteria; approximately 15 with primary liver cancer and 15 with secondary liver cancer. Up to 40 patients may be consented if necessary in order to enroll these 30 patients, to account for potential patients who screen-out or who are unable to complete sample collection for the PK (80% of planned draws). 15 patients will be enrolled into the lobar cTACE arm and 15 patients will be enrolled into the superselective cTACE arm. The assignment of the treatment arm will be determined by the PI or a designated radiologist after review of the patient's imaging and history.

The study is planned to complete enrollment in two years, with another month to conclude patient follow-up.

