### 1.5 Lobar and Superselective TACE

The lobar conventional TACE approach consists of the administration of chemotherapy and Lipiodol to via the left or right hepatic lobar branch followed by embolization. As a consequence of this approach, a large region of the liver is treated which would make it suitable for cases where there are multiple lesions within a lobe. However, this technique was also correlated to a high serum concentration of the chemotherapeutic drug after administration, which compared unfavorably to an alternate form of treatment, the drug-eluting bead TACE (DEBTACE).

While the lobar technique is still very much in use today, TACE protocols have been refined and new specialized protocols developed. The superselective approach would advance the microcatheter further into the hepatic arterial branch afferent to the segment in which the tumor is located, or if possible the tip of the catheter will be further advanced into the subsegmental branches feeding the tumor, where chemotherapy will be administered followed by embolization. In this manner, the chemotherapy is delivered in a more selective fashion, sparing more of the healthy liver parenchyma.

Logistically, the superselective approach introduces new complexities including a lengthier operation and being more technically demanding, but some studies have observed that the superselective approach may result a higher rate of complete tumor necrosis with small HCCs in comparison to the lobar approach (27-29). In Golfieri's study, tumor necrosis was greater in the superselective arm vs the lobar arm (75.1% vs 52.8%), and complete tumor necrosis was observed in approximately two times more patients on the selective arm when compared to the lobar nonselective arm, which also resulted in a reduced need for further treatments (27). The damage to liver parenchyma and function was also reduced with the superselective approach, with less adverse events when compared to the nonselective TACE (28). A superselective or subsegmental approach could also be performed in patients who may be contraindicated for conventional nonselective TACE due to severe cirrhosis and risk of serious ischemic complications (30, 31). Given the reduced adverse event profile of the subsegmental approach and the selective nature of treatment, it is conjectured that the serum doxorubicin concentration would also be decreased.

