## 2. Study Objectives and Endpoints

### 2.1 Primary Objectives/Endpoints

Doxorubicin pharmacokinetics will be performed on all 30 patients. Peripheral blood will be sampled for doxorubicin concentrations just before the cTACE procedure at baseline, and then after cTACE at the following time points: 5 minutes, 10 minutes, 20 minutes, 40 minutes, 1 hour, 2 hours, 4 hours, 24 hours, and 3 or 4 weeks post cTACE. This will be used to construct a pharmacokinetic profile of doxorubicin/doxorubicinol to include:

- Parameters of PK analysis including peak of the plasma concentration ( $C_{max}$ ), time of maximum concentration, and area under the concentration time-curve (AUC).
- PK profiles for each patient will be correlated with toxicity and tumor burden (size of target lesion), BSA and gender.
- Comparison of PK profile between lobar administration and superselective administration.

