## 7. Statistical Methods

### 7.1 Primary Outcome Variable

Pharmacokinetic profile of doxorubicin and doxorubicinol after cTACE for each patient:

- Parameters of PK analysis including peak of the plasma concentration ( $C_{max}$ ), time of maximum concentration, and area under the concentration time-curve (AUC).
- PK profiles for each patient will be correlated with toxicity and tumor burden (size of target lesion), BSA and gender.
- Comparison of PK profile between lobar administration and superselective administration.

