### 7.3 Statistical Plan

Up to 40 patients may be consented in order to enroll 30 patients, and to account for patients who are unable to complete sample collection for the PK (80% of planned draws). 15 patients will be enrolled into the lobar cTACE arm and 15 patients will be enrolled into the superselective cTACE arm.

We have assumed a clinically significant change in doxorubicin exposure would be 50%. In order to have 80% power to detect a 50% change with a 5%  $\alpha$ , the sample size varies depending on the variability noted with TACE therapy. In the Varella trial utilizing cTACE with a Lipiodol doxorubicin formulation, the variability was reported as 30% Coefficient of Variation (CV). In our recent trial (J1306) utilizing TACE with a Drug Eluting Bead (DEB) doxorubicin formulation, the variability was reported as 90% CV. We anticipate the Lipiodol formulation to behave more like the Varella trial with 15 patients allowing for slightly higher variability.

*%CV	30%	43%	90%
Expected Sample Size	8	15	58

\*Methodology/calculator accessed from the websites below on 11/6/2014:

[https://www.statstodo.com/SSizBioequiv\\_Tab.php](https://www.statstodo.com/SSizBioequiv_Tab.php)

[https://www.statstodo.com/SSizBioequiv\\_Pgm.php#](https://www.statstodo.com/SSizBioequiv_Pgm.php#)

Continuous variables will be reported as means and standard deviations, medians and ranges, or both. Categorical variables will be reported as numbers and percentages. Pharmacokinetic parameters will be calculated by standard noncompartmental methods using Phoenix WinNonlin 6.1 (Pharsight, Mountain View, CA) for each patient. Pharmacokinetic parameters will be summarized using descriptive statistics.

Comparisons of the pharmacokinetic profiles between the lobar cTACE group and the superselective cTACE group will be performed using the Mann-Whitney U test. Correlations between pharmacokinetic profiles and clinical toxicities will be performed using the Kruskal-Wallis one-way ANOVA test. Correlations between the pharmacokinetic profiles and tumor burden will be performed with the Spearman's correlation coefficient. A P value < 0.05 will be considered statistically significant in all cases.

HIC #: 1506016008  
[name]

Interim analysis:

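### The lobar versus superselective PK comparison is tested only unadjusted, although the arm is chosen from imaging and history; a supportive burden-adjusted estimate, a by-arm table and a non-randomised interpretation should be added

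*Combined protocol and SAP*

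**What the plan says.** All references are to the combined protocol and SAP.

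- **Assignment.** Section 5.1: "The assignment of the treatment arm will be determined by the PI or a designated radiologist after review" of imaging and history. The flow chart in section 5.2 repeats this and allows 8 to 20 patients per arm around the target of 15.
- **Link between disease extent and technique.** Section 1.5 says of the lobar approach that "a large region of the liver is treated which would make it suitable for cases where there are multiple lesions within a lobe".
- **Status of the comparison.** Section 2.1 lists, among the primary objectives, "Comparison of PK profile between lobar administration and superselective administration". The synopsis and section 7.1 do the same.
- **Analysis.** Section 7.3: "Comparisons of the pharmacokinetic profiles between the lobar cTACE group and the superselective cTACE group will be performed using the Mann-Whitney U test", at P < 0.05. No other analysis of the arm contrast is named.
- **Tumour burden.** Section 7.1: "PK profiles for each patient will be correlated with toxicity and tumor burden (size of target lesion), BSA and gender". Section 7.3: "Correlations between the pharmacokinetic profiles and tumor burden will be performed" with Spearman's coefficient, separately from the arm comparison.
- **Reporting.** Section 7.3 promises general descriptive statistics. No baseline table by arm is named, and no passage limits the interpretation on account of non-random assignment.
- **Purpose.** The synopsis says that no hypothesis drives the study. It also asks whether superselective treatment lowers serum exposure and says that the results could alter practice and technical guidance.

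**The concern.** Disease extent can influence which technique a patient receives, and the protocol itself treats tumour burden as something that may relate to exposure. A variable tied to both arm and outcome is a potential confounder of the arm contrast. The Mann-Whitney test compares the two groups as they stand. A separate burden-PK correlation does not adjust that comparison, and pooling the arms mixes the burden relation with any technique effect.

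Followed exactly, the plan can credit technique with a difference that comes from disease extent. If higher burden lowers exposure, it can instead understate a real technique effect. This matters because the comparison has a primary place, a significance threshold, a powered sample size ("In order to have 80% power to detect a 50% change") and a stated possible influence on practice.

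**Working it through.** **1. The plan's own sample size.** Section 7.3 gives 8, 15 and 58 for CVs of 30%, 43% and 90%, read here as patients per arm. A two-group equivalence formula with a 50% margin, n = 2(CV/0.5)²(t₀.₉₅ + t₀.₉₀)², gives 8, 14 and 57. A two-sided difference formula on the log scale, n = 2[SD_log(1.960 + 0.842)/ln 1.5]², gives 9, 17 and 57. Both are close to the table, which is not at issue here. Either formula covers sampling variability only, not a systematic difference between the arms.

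**2. Inputs for the illustration.**

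| Input | Value | Source |
|---|---|---|
| Patients per arm | 15 | section 7.3 |
| CV | 43% | section 7.3 table, entry for 15 |
| SD of log AUC | √ln(1 + 0.43²) = 0.412 | arithmetic |
| Burden difference between arms, d | 0.5, 1, 1.5 SD | assumption |
| Within-arm correlation of burden with log AUC, ρ | ±0.3, ±0.5, ±0.7 | assumption |

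Model: log AUC = 0.412[ρ × burden + √(1 − ρ²) × noise] + ln(effect) × arm, with burden shifted by d in the lobar arm. The test is the exact two-sided Mann-Whitney test, with 10,000 simulated trials per cell for sections 3, 5 and 6.

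**3. No technique effect, burden raises exposure.** The spurious lobar/superselective ratio is exp(0.412ρd).

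| d | Rejection rate, ρ = 0.3 / 0.5 / 0.7 | Spurious ratio |
|---|---|---|
| 0.5 | 6 / 9 / 14% | 1.06 / 1.11 / 1.16 |
| 1 | 11 / 24 / 42% | 1.13 / 1.23 / 1.33 |
| 1.5 | 20 / 48 / 76% | 1.20 / 1.36 / 1.54 |

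Hand check at d = 1, ρ = 0.5: the expected log difference is 0.412 × 0.5 = 0.206 and its standard error is 0.412√(2/15) = 0.150. The shift is therefore 1.37 standard errors, and a normal approximation gives about 28%. The simulated 24% is lower because the exact Mann-Whitney test has a true size of 4.5% and is slightly less efficient. With no imbalance the test rejects in about 4.5% of trials.

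**4. True technique effect, burden lowers exposure.** Section 7.3 does not say whether the 50% change is a rise or a fall, so both readings are shown (4,000 trials per cell for the ratio of 2.0).

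| d | Power, ratio 1.5 | Power, ratio 2.0 (a 50% reduction) |
|---|---|---|
| 0 | 70% | 99% |
| 0.5 | 56 / 46 / 35% | 97 / 95 / 91% |
| 1 | 40 / 23 / 11% | 94 / 84 / 71% |
| 1.5 | 27 / 8 / 5% | 89 / 67 / 36% |

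**5. Unequal arms.** With 10 and 20 patients, which section 5.2 allows, the false-positive range is 6-72%. Power for a ratio of 1.5 falls from 66% to 53-5%.

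**6. What adjustment achieves.** The model has log AUC as outcome, with arm and one burden covariate (27 residual degrees of freedom).

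| Correlation of covariate with the burden that drove assignment | False positives | Power, ratio 1.5, burden lowering exposure |
|---|---|---|
| 1 | about 5% | 57-93% |
| 0.7 | 5-29% | 22-66% |
| 0.5 | 6-53% | 8-62% |
| 0 | 7-78% | no bias removed |

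With no imbalance and a covariate unrelated to PK, power for a ratio of 1.5 is 70% for Mann-Whitney, 74% for an unadjusted t-test on log AUC and 72% for the adjusted model.

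**The case against.** The strongest reply has five parts.

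- **The magnitude is assumed.** No passage gives the imbalance or the correlation. At 0.5 SD the false-positive rate is only 6-14%; figures near 76% need both extremes. This stands, and the table shows a range, not a forecast.
- **The masking argument depends on the effect size.** The synopsis asks about lower exposure with superselective treatment and section 1.5 conjectures a decrease. A 50% reduction is a ratio of 2.0, for which power starts at 99% and stays above 80% except at larger imbalances and correlations. This stands; masking is a much weaker worry under that reading.
- **The covariate may miss the confounder.** Section 1.5 ties technique to lesion number, while section 7.1 defines burden as target-lesion size. If the arms barely overlap, a model on 30 patients extrapolates. This stands, so the model should be supportive and lesion number must appear in the by-arm table.
- **Something relevant is already planned.** The Spearman correlation bears on the sign of the burden-PK relation, and descriptive statistics are promised. True, but neither adjusts the contrast, and no by-arm presentation is named.
- **The setting is modest.** This is a Phase I study that declares itself without a hypothesis, discloses how arms are assigned and never claims randomisation. That lowers the stakes but does not supply the missing estimate or caveat.

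A reader might infer more than the documents support. They do not show that the comparison is biased, or in which direction. Titration of the amount given to the area treated (section 5.1.1) is partly a consequence of technique and is not in itself evidence of confounding. Liver function is a lesser route: section 1.5 mentions severe cirrhosis, but section 3.2 requires "Preserved liver function (Child-Pugh A-B class) without significant liver decompensation", and section 3.3 excludes bilirubin above 3.0 mg/dL and more than trace ascites. No passage ties tumour type to the choice of arm.

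**Conclusion.** The concern holds as a gap in the analysis plan. A primary-outcome comparison between arms chosen on clinical grounds is tested only unadjusted, so a difference in disease extent can pass for a technique effect or conceal one. What is established is the mechanism and the missing safeguard; the size is illustrative. At an assumed 1 SD imbalance, a nominal 5% test would reject in 11-42% of trials with no technique effect. Loss of power is severe for a 1.5-fold difference but limited for a halving unless imbalance and correlation are both large.

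It would also be too strong to say that adjusting for lesion size solves the problem. It restores about 5% false positives only if lesion size captures the burden that drove assignment; at a correlation of 0.7 up to about 29% remain. The change is advisable because it is cheap and more convincing if fixed before the PK data are seen. It is not a reason to regard the study as unsound.

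**What to change.** In section 7.3, keep the Mann-Whitney test and add the following:

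1. **A prespecified supportive analysis.** Fit one linear model each for doxorubicin log AUC and log Cmax, with arm and log target-lesion size. Report the adjusted geometric mean ratio with its 95% CI beside the unadjusted result. The same models for doxorubicinol are secondary, where values are quantifiable.
2. **Delivered dose kept out of the model**, because it is partly a consequence of technique. Show dose-normalised AUC and Cmax as supporting results only.
3. **A by-arm table** of lesion size, lesion number, tumour type, liver function, BSA and delivered dose.
4. **An interpretation rule.** State the result as a non-randomised association with residual confounding possible. Do not attribute a difference to technique if the adjusted and unadjusted estimates disagree materially, or if the arms overlap little in lesion size or number.

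The cost is SAP wording, a few models and one table, with no extra patients, visits or procedures. Lesion number is not named as a recorded item but can be read from the screening MRI or CT required by section 4.3, which is a small abstraction task. The statistical price is some loss of precision when burden is imbalanced; with no imbalance it is negligible (72% power for the adjusted model against 70% for Mann-Whitney, at a ratio of 1.5).
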